Abnormalities in clinical laboratory tests that lead to a change in subject management (e.g., dose delay, discontinuation, requirement for additional medication or monitoring) are considered clinically significant for the purposes of this study, and will be recorded on the AE eCRF page. With the exception of LFTs, laboratory results will be classified using the Toxicity Grading Scale for Healthy Adult and Adolescent Volunteers Enrolled in Preventive Vaccine Clinical Studies (see Appendix A). Laboratory results for ALT, AST, alkaline phosphatase, GGT, and

bilirubin will be classified according to Table 9-2 in Section 9.4. If laboratory values constitute part of an event that meets criteria defining it as serious, the event (and associated laboratory values) must be reported as an SAE (see Section 11.3.1).

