### **8.2.1 Adverse Events Stopping Criteria**

- AEs of clinical concern
- Grade 2 (moderate) or higher TEAEs that are determined by the investigator to be possibly, probably, or definitely related to study drug (with the exception of liver-related adverse events, see Section 9.4);
- Clinically significant elevation of ALT or AST. See Section 9.4 for risk management of LFTs changes observed during the study.

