## 9.4 Evaluation of Liver-Related Blood Tests

Clinically significant elevations of liver-related blood tests as defined below require immediate drug termination.

1. ALT or AST  $> 5 \times$ ULN
2. ALT or AST  $> 3 \times$ ULN and (total bilirubin  $> 2 \times$ ULN or INR  $> 1.5$ )
3. ALT or AST  $> 3 \times$ ULN with the appearance of fatigue, nausea, vomiting, right upper quadrant pain or tenderness, fever, rash, and/or eosinophilia ( $> 5\%$ )
4. If the total bilirubin is  $> 2 \times$ ULN then obtain direct bilirubin

If ALT or AST  $> 2.0 \times$ ULN, the subject should remain on study drug with **close observation** which includes:

1. Repeating liver enzyme, every 48 to 72 hours  
(Frequency of retesting can decrease to once a week or less if abnormalities stabilize or the study drug has been discontinued and the subject is asymptomatic.)
2. Obtaining a more detailed history of symptoms and prior or concurrent diseases

3. Obtaining a history of concomitant drug use (including nonprescription medications and herbal and dietary supplement preparations), alcohol use, recreational drug use, and special diets
4. Ruling out acute viral hepatitis types A, B, and C
5. Obtaining a history of exposure to environmental chemical agents

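### Protocol Section 9.4 gives opposite drug instructions for every ALT/AST value on its termination list, and does not say whether bilirubin above 2 × ULN alone ends treatment

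*Protocol*

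**What the plan says.** Protocol Section 9.4 contains a list and then a separate instruction.

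The list is introduced by: "Clinically significant elevations of liver-related blood tests as defined below require immediate drug termination". It has four items:

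1. ALT or AST above 5 × ULN.
2. ALT or AST above 3 × ULN together with total bilirubin above 2 × ULN or INR above 1.5.
3. ALT or AST above 3 × ULN "with the appearance of fatigue, nausea, vomiting, right upper quadrant pain or tenderness, fever, rash, and/or eosinophilia" above 5%.
4. If total bilirubin is above 2 × ULN, "then obtain direct bilirubin".

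The instruction after the list says that if ALT or AST is above 2.0 × ULN, "the subject should remain on study drug with" close observation. Close observation starts with repeat liver enzymes every 48 to 72 hours. A parenthesis lets retesting become less frequent if the abnormalities stabilize, "or the study drug has been discontinued and the subject is asymptomatic".

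Other sections defer to this one. Section 8.2.1 lists as a stopping criterion: "Clinically significant elevation of ALT or AST. See Section 9.4 for risk management of LFTs changes observed during the study". Section 7.2.15 refers increases above 2 × ULN to Section 9.4. The note under Table 9-2 says that this evaluation is to guide the stopping rules. The SAP contains no liver stopping rule.

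**The concern.** Section 9.4 is the rule by which sites decide whether a subject with raised liver tests stops drug. As printed, one sentence requires termination and the next tells the site to continue, and the second has neither an upper limit nor an exception for subjects who meet the first. Item 4 adds a separate uncertainty: it stands under a lead-in about termination but prescribes only a test.

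The stake is first of all subject safety. Section 4.3 reports raised ALT/AST as the only adverse experience in the earlier 36-subject, three-cohort psoriasis study, in about 20% of subjects. Two sites could apply Section 9.4 differently to the same result, and each could point to the text.

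**Working it through.** The plan states no figure on this point, so there is nothing to reproduce. The check is whether the two instructions, taken as written, can apply to the same subject.

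**Inputs (all from Section 9.4).** Let x be ALT or AST, and b total bilirubin, both in multiples of ULN. Let i be INR, and s the presence of a listed symptom or eosinophilia above 5%.

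- Terminate (items 1 to 3): x > 5, or x > 3 with (b > 2 or i > 1.5), or x > 3 with s.
- Remain: x > 2.0.

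**Step 1: can a value require termination without also meeting the remain instruction?** Every branch of the terminate rule needs x > 3, and x > 3 implies x > 2.0. So every terminating value also meets the remain instruction. A check of x from 0 to 19.9 in steps of 0.1, with each co-factor present and absent, found no exception.

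**Step 2: where do both apply?**

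| ALT or AST (× ULN) | Co-factor in item 2 or 3 | Terminate (items 1–3) | Remain | Conflict |
|---|---|---|---|---|
| up to 2.0 | any | no | no | no |
| above 2.0 to 3 | any | no | yes | no |
| above 3 to 5 | absent | no | yes | no |
| above 3 to 5 | present | yes | yes | **yes** |
| above 5 | any | yes | yes | **yes** |

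**Step 3: item 4.** Two readings are open. Under the lead-in, total bilirubin above 2 × ULN would itself be a ground for termination at any ALT/AST. By its own words, the item is a work-up step placed in the wrong list. Section 9.4 does not say which.

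**Step 4: is precedence set elsewhere?** Sections 7.2.15 and 8.2.1 and the note under Table 9-2 all lead back to Section 9.4. None says which instruction prevails when both apply.

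**Step 5: can the affected subjects be counted?** The only rate is the roughly 20% in Section 4.3, which is 0.20 × 36 = 7.2, or about 7 subjects. It covers elevated ALT/AST without a breakdown at 2, 3 or 5 × ULN. It also includes the 400 mg BID cohort, which had the highest (Grade 3) elevations and is not a regimen in this trial. If that grade is on the Table 9-2 scale (an assumption), it means above 5 to 10 × ULN, inside the conflict. This shows that such values have probably occurred with this drug, but gives no rate for the present cohorts.

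**The case against.** The best defence is that sensible readers will resolve the overlap. The list uses mandatory wording, while the continuation sentence uses should. Read literally, that sentence would cancel items 1 to 3 altogether, which cannot be what was meant. The retesting parenthesis recognizes that some subjects under observation are already off drug. The note under Table 9-2 also points to the Investigator's Brochure, which is not available here and may say more. On item 4, direct bilirubin is already in the routine chemistry panel (Table 7-1) at every visit, which suggests a drafting slip.

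Much of this stands. Most readers would probably let the termination wording prevail, so the defect is missing precedence wording rather than an unworkable rule. But the protocol does not state that reading. The parenthesis also cuts the other way: the paragraph that orders continuation describes subjects already off drug, so it is not cleanly confined to those who meet none of items 1 to 3. For item 4, the routine panel does not settle whether bilirubin alone ends treatment.

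A reader might also infer a wider conflict, in which every value above 2 × ULN is a stopping criterion. Section 7.2.4 says that laboratory abnormalities leading to a change in management, including a "requirement for additional medication or monitoring) are considered clinically significant for the purposes of this study", and values above 2 × ULN do trigger extra testing. The documents do not support that step. The Section 7.2.4 wording decides what is recorded on the AE page of the eCRF, and its examples include dose delay and monitoring, so it is not a list of stops. Section 8.2.1 sends the reader to Section 9.4, whose lead-in supplies its own definition of a clinically significant elevation.

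**Conclusion.** The point holds within the limits of the table: above 5 × ULN, or above 3 and up to 5 × ULN with a listed co-factor, Section 9.4 requires termination and also tells the site to continue. Separately, the status of total bilirubin above 2 × ULN alone is undefined. The conclusion rests only on the printed wording. How often sites would differ cannot be known from the documents.

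Two larger claims are tempting and are not supported:

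- **A head count.** Applying 20% to the 88 planned KD025 subjects gives 0.20 × 88 = 17.6, but that figure is not a count of subjects in the conflict, for the reasons in Step 5.
- **An effect on the primary result.** SAP Section 3.8.1 counts subjects without a Week 16 assessment as PASI 75 failures, so one extra stop in a cohort of 22 could move its rate by at most 1/22 = 4.5 percentage points. That ceiling needs the subject to have been a responder otherwise. At the 33% planning rate in SAP Section 3.12, the expected shift is 0.33 × 4.5 = 1.5 points. No stop is shown to have turned on this wording, so the effect is speculative.

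The point is still worth acting on, because this is the governing liver-stop rule and the remedy is cheap.

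**What to change.** The sponsor's medical lead should reconcile the two instructions in Section 9.4 by stating which one governs when a value meets both. The same clarification should say whether item 4 is a termination criterion or a work-up step, and place it accordingly. Sections 7.2.15 and 8.2.1 and the note under Table 9-2 can keep pointing to Section 9.4 once it is unambiguous. No threshold or clinical rule is proposed here.

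Protocol Section 12.2 and SAP Section 3.12 say that the study was terminated early with 110 subjects, so a change of wording may come too late to affect dosing. If dosing has finished, the sponsor should document which reading was applied to each liver-related stop.

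The cost is a short protocol clarification, with no new tests or visits.

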**Table 9-2: Grading of Liver-Related Laboratory Abnormalities**

FEATURE	Grade 0	Grade 1	Grade 2	Grade 3	Grade 4
ALT	<1.25 ULN	1.25-2.5 ULN	>2.5-5.0 ULN	>5.0-10 ULN	>10 ULN
AST	<1.25 ULN	1.25-2.5 ULN	>2.5-5.0 ULN	>5.0-10 ULN	>10 ULN
Alkaline Phosphatase	<1.25 ULN	1.25-2.5 ULN	>2.5-5.0 ULN	>5.0-10 ULN	>10 ULN
GGT	<1.25 ULN	1.25-2.5 ULN	>2.5-5.0 ULN	>5.0-10 ULN	>10 ULN
Bilirubin	Normal	>1.0-1.5 ULN	>1.5-2.5 ULN	>2.5-5 ULN	>5 ULN

Abstracted from: CDER-PHARMA-AASLD Conference 2000, Dufour 2000a and Dufour 2000b.

Note: A Grade 2 elevation of ALT, for example, does not connote a Grade 2 TEAE and the above evaluation should guide stopping rules.

For further details, see IB 2015, Summary of Data and Guidance for the Investigator.

### 9.5 Identity of Investigational Products

**Table 9-3 Investigational Products**

Product	Strength	Dosage Form	Route
KD025	200 mg	Yellow to pale yellow oval shaped tablet	Oral
Placebo		Yellow to pale yellow oval shaped tablet	Oral

KD025 and placebo will be supplied by Kadmon.

### 9.6 Study Drug Packaging and Labeling

KD025 and placebo will be packaged and labeled by the sponsor or designee. The label attached to each bottle will provide the following information:

- Description of contents (number and strength of tablets) and route of administration
- Directions for use

- Storage conditions
- Product identification code
- Lot number identification
- Bottle number
- Name of protocol sponsor
- The statement, “Caution: New Drug – Limited by Federal Law to Investigational Use”
- The statement, “Keep out of the reach of children and pets”

### **9.7 Dispensing of Study Drug and Dosing Compliance**

The amount of study drug dispensed to the subject at the beginning of each dosing month should be sufficient to allow for 1 month of dosing. In the 32-week continuation period, the amount of KD025 dispensed at each visit will be sufficient to allow for dosing until the next visit.

The investigator (or designee) will be responsible for recording this information on the appropriate study drug inventory. This inventory will be maintained throughout the duration of the study and will be periodically reviewed by a representative of the sponsor.

The investigator (or designee) will instruct the subject that all dispensed bottles must be returned at each follow-up visit, at which time a tablet count will be conducted to assure subject dosing compliance.

Additionally, subjects will be required to keep study drug diaries in which they will record the details of study drug administrations. These diaries will be dispensed and/or collected according to the Schedule of Assessments (Table 1-1).

### **9.8 Study Drug Storage**

All supplies of study drug are to be stored at United States Pharmacopeia controlled room temperature of 20°C to 25°C (66°F to 77°F) with excursions permitted between 15°C and 30°C (59°F and 86°F). At the clinic, the study drugs are to be stored in a securely locked area, accessible to authorized persons only, until needed for dosing.

### **9.9 Study Drug Accountability**

The US FDA and other regulatory agencies require accounting for the disposition of all investigational drugs received by each clinical site. Information on drug disposition required by law consists of the date received, date administered, quantity administered, and the subject to whom the drug was administered. The principal investigator is responsible for the accounting for all unused study drugs and all used study drug containers. The investigator must maintain a complete and current dispensing and inventory record that has been supplied by the sponsor.

### **9.10 Study Drug Handling**

At the termination of the study, a final drug accountability review and reconciliation must be completed and any discrepancies must be investigated and their resolution documented.

#### **9.10.1 Disposition of Used Supplies**

At the completion of a subject's participation in the study, all partially used and empty pill bottles must be returned to the investigator (or designee) so that a final subject-dosing inventory may be conducted. This information will be recorded on the Drug Dispensing Log.

#### **9.10.2 Inventory of Unused Supplies**

Periodically throughout and at the conclusion of the study, an inventory of unused bottles of study drug will be conducted by a representative of the sponsor.

## 10 CONCOMITANT MEDICATION AND TREATMENT

Subjects will be counseled to avoid non-prescribed medicines or complementary alternative medicines excluded by the study. Any medications a subject receives from signing ICF through the end of study (30-Day Follow-Up visit) will be documented. After discontinuation of study drug, any concomitant medication used in response to an AE is to be recorded on the appropriate eCRF.

Administration of acid-reducing medications should be avoided during the study as these agents may decrease exposure to KD025. If acid-reducing agents are needed, H-2 antagonists or antacids will be recommended rather than proton pump inhibitors. Administration of acid-reducing agents such as H-2 antagonists or antacids, if required, should take place no less than 2 hours before or after dosing with KD025.

Subjects may be receiving low-dose oral corticosteroids ( $\leq 10$  mg daily prednisone or equivalent) at study entry. Oral corticosteroid dose must be stable for at least 1 month prior to study entry and expected to remain stable throughout participation. Any changes in systemic corticosteroid dose will be documented on the eCRF. Topical corticosteroids or immunosuppressive therapies to the face, groin, or scalp are allowed.

Prior systemic treatment, including biologics, is to be recorded on the eCRF, including duration of exposure and reason for discontinuation.

The concomitant medication names will be coded by the sponsor according to the World Health Organization (WHO) Drug Dictionary and classified by anatomical therapeutic chemical (ATC) categories.

## **11 SAFETY**

### **11.1 Safety Parameters**

The Clinical Symptom and Adverse Event Grading Scale will be used for grading toxicities (see Appendix E). With the exception of LFTs, laboratory results will be classified using the Toxicity Grading Scale for Healthy Adult and Adolescent Volunteers Enrolled in Preventive Vaccine Clinical Studies (see Appendix A). LFTs will be classified using Table 9-2 in Section 9.4. Subjects will be monitored throughout the treatment and follow-up period for occurrence of AEs, as well as for changes in clinical status, vital sign measurements, and laboratory data.

### **11.2 Adverse Event Definition**

An AE is defined as any untoward medical occurrence associated with the use of a drug in humans, whether or not considered drug related. AEs include:

- Suspected adverse drug reactions (abbreviated as either SADR or SAR). This may be serious or not serious
- Reactions from drug overdose, abuse, withdrawal, sensitivity, or toxicity
- Significant changes or abnormalities, when compared with baseline, in structure (sign), function (symptom), clinical laboratory results, ECG results, or physiological testing. This includes any worsening of a pre-existing condition temporally associated with the use of study drug
- Other medical events, regardless of their relationship to the study drug, such as injury, surgery, accidents, extensions of symptoms, or apparently unrelated illnesses

For the purpose of data collection, all untoward events that occur after ICF through 30 days after last dose of study treatment are to be recorded on eCRFs by the investigational site.

### **11.3 Evaluating Adverse Events**

The investigator will determine the seriousness, intensity, and causality of an AE associated with the use of the study drug (i.e., events where there is a reasonable possibility that the event may have been caused by the study drug) based on the definitions that follow.

### 11.3.1 Serious Adverse Events

(Notify sponsor or designee within 24 hours; document on eCRF)

The SAE definition and reporting requirements are in accordance with Title 21 Part Code of Federal Regulations (CFR) 312.32 and the Guidance for Industry and Investigators Safety Reporting Requirements for Investigational New Drug (IND) applications and bioavailability/bioequivalence (BA/BE) studies.

SAE: An adverse event is considered “serious” if, in the view of either the investigator or sponsor, it results in any of the following outcomes:

- **Death:** This includes any death that occurs while the subject is “on study” as well as any death that occurs within 30 days after study drug administration.

**Note:** Death is an outcome of an AE, and not an AE in itself. The event(s) that caused death (e.g., illness, accident) is the SAE. Death due to any other cause(s) must also be reported as an outcome of the reportable SAE.

- **Life-threatening AE:** An AE or suspected adverse reaction is considered “life-threatening” if, in the view of either the investigator or sponsor, its occurrence places the subject at immediate risk of death. It does not include an AE or suspected adverse reaction that, had it occurred in a more severe form, might have caused death.

- **Inpatient hospitalization or prolongation of existing hospitalization:**

In the absence of an AE, the investigator should not report hospitalization or prolongation of hospitalization. This is the case in the following situations:

- Hospitalization or prolongation of hospitalization is needed for a procedure required by the protocol
- Hospitalization or prolongation of hospitalization is part of routine procedure followed by study center
- Hospitalization for survey visits or annual physicals

In addition, a hospitalization planned before the start of the study for a pre-existing condition which has not worsened does not count as an SAE.

- **Persistent or significant incapacity or substantial disruption of the ability to conduct normal life functions**
- **Congenital anomaly/birth defect**
- **Important medical event:** An event that may not result in death, be life threatening, or require hospitalization may be considered serious when, based upon appropriate medical judgment, it may jeopardize the subject and may require medical or surgical intervention to prevent 1 of the outcomes listed in this definition.

### **11.3.2 Suspected Unexpected Serious Adverse Reaction**

(Notify sponsor or designee within 24 hours of first awareness; document on eCRF)

A suspected unexpected serious adverse reaction (SUSAR) is any adverse drug event, the specificity or severity of which is not consistent with those noted in the current protocol and/or IB. This refers to any AE that has not been previously observed (e.g., included in the IB), rather than from the perspective of such an event not being anticipated from the pharmacological properties of the product.

### **11.3.3 Unexpected Adverse Events**

An AE is considered “unexpected” if it is not listed in the IB or is not listed at the specificity or severity that has been observed; or, if an IB is not required or available, is not consistent with the risk information described in the General Investigational Plan or elsewhere in the current application. The term also refers to AEs that are mentioned in the IB as occurring with a class of drugs or as anticipated from the pharmacological properties of the drug, but are not specifically mentioned as occurring with the particular drug under investigation.

### **11.3.4 Non-Serious Adverse Events**

All other AEs, not fulfilling the previous definitions, are classified as non-serious.

### **11.3.5 Protocol-Related Adverse Events**

AEs that are not study drug related may nevertheless be considered by the investigator or the medical monitor to be related to the conduct of the clinical study. That is, the event may be related to the fact that a subject is participating in the study. For example, a protocol-related AE

may be an event that occurs during a washout period or that is related to a procedure required by the protocol.

### **11.3.6 Relationship to Study Drug**

The investigator will attempt to assess the relationship of the event to study drug using a 5-point scale (not related, unlikely related, possibly related, probably related, or definitely related; see Appendix F; Clinical Adverse Events: Determining Relationship to Study Drug).

### **11.3.7 Recording Adverse Events**

All AEs (including SAEs) are to be accurately recorded on the Adverse Event page of the subject's eCRF during the subject's participation in the study. The severity of each AE will be graded using a 5-point scale (mild, moderate, severe, life threatening, or death; see Appendix E). The date of onset as well as the end date of the event also should be recorded or the event should be entered as "ongoing". In addition, the method used to treat the AE and the outcome of the AE also will be noted. The investigator will assess the relationship of the event to study drug.

### **11.3.8 Hospitalization**

In the absence of an AE, the investigator should not report hospitalization or prolongation of hospitalization. This is the case in the following situations:

- Hospitalization or prolongation of hospitalization is needed for a procedure required by the protocol.
- Hospitalization or prolongation of hospitalization is part of routine procedure followed by study center.
- Hospitalization for survey visits or annual physicals.

In addition, a hospitalization planned before the start of the study for a pre-existing condition that has not worsened does not count as an SAE.

